#### Comments:

An independent statistical development plan will be developed to provide further details. Due to the overall small N, the ability to perform subgroup analyses for confounding, sensitivity, etc. is limited.

| Section 11: Data management and guality control   | Yes | No          | N/A | Section
Number |
|---|-----|-------------|-----|-------------------|
| 11.1 Does the protocol provide information on data
storage? (e.g. software and IT environment, database
maintenance and anti-fraud protection, archiving) |     |             |     | 7.6, 7.8.2        |
| 11.2 Are methods of quality assurance described?  | X   |             |     | 7.8               |
| 11.3 Is there a system in place for independent review
of study results?   |     | $\boxtimes$ |     |                   |

#### Comments:

Results will be communicated to applicable health authorities within the agreed timeframe.

| Section 12: Limitations  | Yes | No | N/A | Section
Number |
|--|-----|----|-----|-------------------|
| 

12.1 Does the protocol discuss the impact on the study results of:

12.1.1 Selection bias?

12.1.2 Information bias?

 |     |    |     | 7.9               |

| Section 12: Limitations   | Yes | No | N/A | Section
Number |
|---|-----|----|-----|-------------------|
| 12.1.3 Residual/unmeasured confounding?
(g.g. anticipated direction and magnitude of such biases,
validation sub-study, use of validation and external data,
analytical methods).          |     |    |     |                   |
| 12.2 Does the protocol discuss study feasibility?
(e.g. study size, anticipated exposure uptake, duration of
follow-up in a cohort study, patient recruitment, precision of the
estimates) |     |    |     | 7.5               |

| Section 13: Ethical/data protection issues  | Yes         | No | N/A | Section
Number |
|---|-------------|----|-----|-------------------|
| 13.1 Have requirements of Ethics Committee/
Institutional Review Board been described? | $\boxtimes$ |    |     | 8                 |
| 13.2 Has any outcome of an ethical review procedure
been addressed?                    |             |    | X   |                   |
| 13.3 Have data protection requirements been
described?                                 | $\boxtimes$ |    |     | 8                 |

#### Comments:

| Section 14: Amendments and deviations  | Yes         | No | N/A | Section
Number |
|--|-------------|----|-----|-------------------|
| 14.1 Does the protocol include a section to document
amendments and deviations? | $\boxtimes$ |    |     | 3                 |

## Comments:

| •  |     |    |     |                   |
|--|-----|----|-----|-------------------|
| Section 15: Plans for communication of study
results  | Yes | No | N/A | Section
Number |
| 15.1 Are plans described for communicating study results (e.g. to regulatory authorities)?     | X   |    |     | 10                |
| 15.2 Are plans described for disseminating study results
externally, including publication? | X   |    |     | 10                |

#### 12.3 Annex 3 – Additional information

None.

## 13 Appendices

## 13.1 Appendix – HCP Survey questionnaire

#### SURVEY QUESTIONNAIRE

Note to Reviewers:

- 1. Items in **RED** font are programming instructions and will not be seen by HCPs who complete the survey.
- 2. Items in *italics* are information for questionnaire reviewers and will also not be seen by HCPs who complete the survey.

Please enter your Unique ID to participate in the survey. Your Unique ID was provided in your survey invitation.

Unique ID: \_\_\_\_\_ → IF ENTERED, PROCEED TO COUNTRY AND LANGUAGE SELECTION, OTHERWISE, TERMINATE SURVEY

The above section will only appear for respondents who did not receive their invitation directly by email from the survey software.

Surveys sent by post will include a unique ID in their invitation letter, which will need to be entered.

Correct responses are ticked as  $\checkmark$  and will be removed for the versions used for pre-testing and the actual survey.

Key questions for the primary endpoint are noted in brackets.

Please select your country and preferred language from the list below:

| □ Country 1 (language or English) | → PROCEED TO SURVEY INTRODUCTION |
|-----------------------------------|----------------------------------|
| Country 2 (language or English)   | → PROCEED TO SURVEY INTRODUCTION |
| Country 3 (language or English)   | → PROCEED TO SURVEY INTRODUCTION |
| □ Country 4 (language or English) | ➔ PROCEED TO SURVEY INTRODUCTION |
| Country 5 (language or English)   | → PROCEED TO SURVEY INTRODUCTION |
| □ Country 6 (language or English) | → PROCEED TO SURVEY INTRODUCTION |
| □ My country is not listed        | ➔ THANK AND TERMINATE            |
|                                   |                                  |

[Termination Language for Non-Qualified Candidates:]

Once country/language is selected, the survey introduction is displayed in local language (next page).

#### [Termination Language for Non-Qualified Candidates:]

Thank you for your interest in participating in this survey. However, you are not eligible to complete this survey. We look forward to your potential participation in a future study.

[Language for Qualified Candidates:]

Thank you for your responses. You qualify for this survey. Please click on the NEXT button to proceed to the main survey.

#### [END SURVEY SCREENING QUESTIONS]

#### MAIN SURVEY

[Preamble 1]: These questions are about important product information for Piqray. Please be sure to review all response choices for each question before answering each question.

1. Did you receive the "Piqray Prescriber's/HCP **Guide for Hyperglycemia**" that reminds healthcare professionals about certain how to identify, and manage, hyperglycemia in patients treated with Piqray?

```
🗆 Yes
```

#### □ No → PROCEED TO QUESTION 3

- □ I don't know/am not sure → PROCEED TO QUESTION 3
- 2. Did you read or review the "Piqray Prescriber's/HCP Guide for Hyperglycemia"?
  - Yes, all of it
    Yes, some of it
    No
    I don't know/am not sure
- What is the primary source you use to learn about the indication, precautions for use, and potential risks for Piqray? (please tick only 1 response)

D Piqray Summary of Product Characteristics

- D Piqray Prescriber's/HCP Guide for Hyperglycemia
- National Competent Authority website
- Professional Society or Congress
- □ The Piqray product website
- The European Medicines Agency website
- Clinical practice guidelines
- A representative from Novartis
- □ Other (not listed above)
- □ I do not know/am not sure

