#### 7.3.1 **Outcomes/endpoint variables**

Primary endpoint:

- Levels of knowledge of the risk for hyperglycemia, and risk factors for hyperglycemia, (survey question 4A, 6),
- Levels of knowledge of signs and symptoms of hyperglycemia (survey questions 5A-C), •
- Levels of knowledge of recommendations for monitoring for hyperglycemia prior to, and during, treatment with Pigray (survey questions 8A-C, 10, 15) and
- Levels of knowledge of recommendations for managing hyperglycemia during treatment ٠ with Piqray (survey questions 12-14).

The primary endpoint is a composite endpoint that combines correct responses given by HCPs to questions included in the composite. Specifically, the primary endpoint is a weighted composite knowledge score aggregated across the following survey questions: 4A, 5A-C, 6, 8A-C. 10, and 12-15. It is calculated as the number of all correctly answered questions divided by the number of all answered questions (i.e. questions that were answered either correct and not correct – unanswered questions are excluded).

Success criteria on the primary endpoint is defined as a weighted composite knowledge level of at least 70% across these key questions.

Secondary endpoint questions:

- Levels of reported receipt and reading of the Pigray Prescriber's/HCP Guide for • hyperglycemia, assessed as the percentages of HCPs who report receipt and reading of the same (survey questions 1, 2)
- HCPs' knowledge levels for each survey question regarding knowledge of, and • management of, hyperglycemia, assessed as the percentages of HCPs with correct responses to each question (individual responses to survey questions 4-15)
- The distribution of responses regarding the primary source from which HCPs learned • about the messages included in the Piqray Prescriber's/HCP Guide for Hyperglycemia, assessed as the percentages of HCPs who report using each of the possible sources as the primary source they used (survey question 3).

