## 7.6 Data management

Survey data collection will be completed on-line in Confirmit, a software platform specifically designed for the creation and delivery of multi-lingual surveys. Data collected will be stored at secure servers and will be maintained to ensure compliance with applicable local and national regulations.

Response sets for multiple-choice questions will be randomised to minimize bias. To minimize likelihood that respondents would look up answers and/or discuss the survey while taking it, respondents will be asked to complete survey in one sitting and will not be allowed to revise their answers after they advance to the next question.

Survey database lock is anticipated to occur shortly after the survey is closed in the last country. To reduce opportunity for bias, survey respondents will not be contacted to clarify or revise their responses to knowledge assessment-related questions.

Data management will be in accordance with the standard operating procedures (SOPs).

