 4 weeks after treatment start, then every 3 months thereafter
 Monthly for the first 6 months of treatment, then annually thereafter
 I don't know/am not sure

[ON-LINE SURVEY - PROGRAMMER: RANDOMIZE THE ORDER OF THE FIRST 3 RESPONSE OPTIONS]

 According to the Piqray Prescriber's/HCP Guide for Hyperglycemia and SmPC for Piqray, please indicate if the following statement is True or False: For fasting glucose values that are ≤250 mg/dL (≤13.9 mmol/L), no Piqray dose adjustment is required. It is recommended to manage by initiating or intensifying oral antihyperglycemic treatment.

🖌 True

🗆 False

□ I don't know/am not sure

- 13. According to the Piqray Prescriber's/HCP Guide for Hyperglycemia and SmPC for Piqray, which of the following fasting glucose values (blood) that are elevated (above the upper limit of normal) require Piqray dosing to be interrupted?
  - Any fasting glucose value >160 mg/dL (>8.9 mmol/L)
  - □ Any fasting glucose value >200 mg/dL (>27.8 mmol/L

□ Any fasting glucose value >200 mg/dL (>27.8 mmol/L

Any fasting glucose value >250 mg/dL (>13.9 mmol/L)

□ I don't know/am not sure

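### Two primary-composite items, 4A and Q13, are cued by earlier question stems; the net effect is likely upward, of unfixed and probably modest size, and reordering removes most of it at little cost

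*Protocol*

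**What the plan says.** Protocol section 7.3.1 defines the primary endpoint as a score "aggregated across the following survey questions: 4A, 5A-C, 6, 8A-C. 10, and 12-15". The score is the "number of all correctly answered questions divided by the number of all answered questions", so every answered item carries the same weight. On the decision: "Success criteria on the primary endpoint is defined as a weighted composite knowledge level of at least 70% across these key questions". Section 7.7.2 compares the point estimate with 70% and sets no condition on the confidence bound.

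The questionnaire in Appendix 13.1 gives this sequence:

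- Q1 asks whether the respondent received a guide on "how to identify, and manage, hyperglycemia in patients treated with Piqray". Q2 and one option of Q3 repeat the guide's title.
- Q4 lists risks to be ticked if associated with Piqray. Item 4A, hyperglycemia, is marked as key.
- Q12 is a True/False item, keyed True. It says that at fasting glucose of 250 mg/dL (13.9 mmol/L) or below, "no Piqray dose adjustment is required".
- Q13, the next question, asks which elevated values "require Piqray dosing to be interrupted". The mg/dL options are >160, >200 and >250, and >250 is keyed. Table 7-1 marks Q13 as key.

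Section 7.6 lists the protections for the knowledge measurement: response options are randomised, the survey is taken in one sitting, and respondents "will not be allowed to revise their answers after they advance to the next question".

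**The concern.** The protections in section 7.6 work backwards. They stop a respondent from reading a later stem and returning to correct an earlier answer. This matters because the stem of Q5 again ties hyperglycemia to Piqray, and the stem of Q14 again shows 250 mg/dL. They do nothing when the informative stem comes first, as Q1 does for 4A and Q12 does for Q13. The randomisation notes do not help either: their counts match the rows or options within a question, and the skip from Q1 to Q3 presupposes a set sequence.

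A respondent without prior knowledge may therefore score on 4A from Q1, and on Q13 by staying consistent with a True answer to Q12. At stake is a composite that overstates knowledge of the guide. More respondents would not dilute the error, and the interval plays no part in the success rule.

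**Working it through.** **The plan's own figures.** Exact (Clopper-Pearson) 95% limits at 70% are 50.6 to 85.3 for n = 30 (half-width 17.3) and 55.4 to 82.1 for n = 50 (half-width 13.4). Table 7-4 gives the same limits, with precision 17.4 and 13.4. The gap of 0.1 at n = 30 is rounding. The protocol gives no figure for cueing.

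**Weight of the two items.** Section 7.3.1 names 4A (1), 5A-C (3), 6 (1), 8A-C (3), 10 (1) and 12-15 (4), which makes 13. Table 7-1 and the appendix also mark 5F, 5G and 5H as key, which would make 16. Two items are 2/13 = 15.4% or 2/16 = 12.5% of the composite.

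**Inflation if both cued items reach 100%.** With K items and true (uncued) knowledge p(4A) and p(13):

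inflation = [(1 − p(4A)) + (1 − p(13))] / K

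The true rates are not in the protocol, so those below are assumptions.

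| p(4A) | p(13) | K = 13 | K = 16 |
|---|---|---|---|
| 100% | 100% | 0 | 0 |
| 95% | 70% | 0.35/13 = +2.7 | 0.35/16 = +2.2 |
| 95% | 50% | 0.55/13 = +4.2 | 0.55/16 = +3.4 |
| 50% | 50% | 1.00/13 = +7.7 | 1.00/16 = +6.3 |
| 25% | 25% | 1.50/13 = +11.5 | 1.50/16 = +9.4 |

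With p(4A) = 95%, item 4A adds only 0.05/13 = 0.4 points. The rest comes from Q13.

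**Limiting case.** If every respondent got both items right, the other items would need (0.70 × 13 − 2)/11 = 64.5% for a composite of 70%, or (0.70 × 16 − 2)/14 = 65.7% with 16 items.

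**Allowing for the True/False format of Q12 (13 items, Q13 only).** Let t be the share judging Q12 True and q the uncued knowledge of Q13, taken as equal in both groups.

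- Only those who judge Q12 True are cued, and the others are unaffected: change = t(1 − q)/13. For t = 70%, this is 0.7 × 0.5/13 = +2.7 points at q = 50% and 0.7 × 0.3/13 = +1.6 at q = 70%.
- In addition, everyone who rejects Q12 is steered to a wrong Q13 answer: change = (t − q)/13. For t = 70%, q = 50%, this is 0.2/13 = +1.5 points. For t = 50%, q = 70%, it is −1.5 points.

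The last case is an extreme. Q12 and Q13 rest on the same boundary, so a respondent who knows the keyed answer to Q13 has little reason to reject Q12. Few correct Q13 answers are at risk, while those who guess and accept Q12 gain. A net upward effect is therefore likely but not certain.

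**The case against.** A reader might infer that the survey gives both answers away, that the two items measure only attention to the survey, and that the bias can run only towards success. The documents do not support this.

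- Q12 is a test item with no feedback and a don't-know option. The other three True/False items (Q7, Q9, Q14) are keyed False, so the format gives no reason to trust a stem. Q12 settles Q13 only for those who judge it True, and many of them may know the boundary already. The 64.5% figure is thus a limit, not an expected effective threshold.
- Respondents must have prescribed Piqray within the previous 6 months (section 7.2.1) and come mainly from the guide's dissemination list. Knowledge of 4A is plausibly close to complete without any cue.
- An example that lifts the composite from just under 70% to just over it needs rates that the protocol does not give. The plausible shift is also smaller than the stated precision of 13.4 to 17.4 points.
- In Q6, 250 mg/dL appears as a risk-factor option and says nothing about interruption.
- In Q13, the printed mg/dL and mmol/L values of the >200 option do not correspond. Someone reading only mmol/L could not rule it out from Q12. That option must be reconciled in any case.

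All of this stands and limits the size. Three further arguments carry less weight. Percent correct per question is a secondary endpoint, so a reader can see 4A and Q13 separately, but a cued answer cannot be uncued in analysis, and section 7.6 rules out recontact on knowledge questions. The appendix mentions pre-testing, but not that it looks for cueing. Reversing Q12 and Q13 could lead someone who picks >250 to answer Q12 True, but that cue is the respondent's own choice among several displayed values, which is weaker than a single value supplied by the survey.

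**Conclusion.** The point holds in limited form. Two items of the primary composite are preceded by stems that cue them, and the no-revision rule does not reach forward cues. The 4A cue is direct but probably worth little among recent prescribers. The Q13 cue is strong, conditional on judging Q12 True, and carries most of any effect.

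The net effect is likely upward. On a 13-item composite with cued items rising to 100%, it is about +2.7 to +4.2 points if 4A is known by 95% and Q13 by 50% to 70%. It is near zero if both are already known, and +11.5 points if only 25% know each. It is smaller if 16 items count, or if only those who accept Q12 are cued. All knowledge rates are assumptions, and the protocol supports no single figure. It also does not support a conclusion that the 70% criterion would be met falsely. This is a worthwhile, low-cost improvement before launch, not a must-fix.

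**What to change.** 1. Show Q13 before Q12 and keep it before Q14. The existing no-revision rule then protects it.
2. Show Q4 before Q1 to Q3. Those three concern receipt, reading and source of information, and lose nothing by coming later.
3. The survey's subject may disclose 4A whatever the order, so also report the composite without 4A as a sensitivity result.

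The cost is minor reprogramming and a check of the skip from Q1 to Q3. If the present numbers are kept as item labels and only the display order changes, the item references in section 7.3.1 and Table 7-1 can stay. No questions or respondents are added. The composite may come out slightly lower, and some consistency between a respondent's own Q13 and Q12 answers will remain.

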## [ON-LINE SURVEY - PROGRAMMER: RANDOMIZE THE ORDER OF THE FIRST 8 RESPONSE OPTIONS]

| Novarti   | is                              | Confidential  |                               |
|---|---------------------------------|---|-------------------------------|
| Non-In  | terventional Study Protocol v00 |   | BYL719/alpelisib/CBYL719C2005 |
| 
 
Listed below are several risks.
Piqray?
 
 |                                 | ich of these risks are asso                           | ciated with treatment with    |
|   |                                 | Check the box if
associated with
treatment with |                               |

|   |                              | Piqray |
|---|------------------------------|--------|
| А | Hyperglycemia [KEY QUESTION] | 1      |
| В | Pneumonitis                  | 1      |
| С | Severe cutaneous reactions   | 1      |
| D | Suicidal ideation            |        |
| Е | Onychomycosis                |        |
| F | I don't know/am not sure     |        |

#### [ON-LINE SURVEY - PROGRAMMER: RANDOMIZE THE ORDER OF THESE 5 QUESTIONS]

5. Hyperglycemia is a reversible, on target effect of treatment with Piqray. Which of the following signs and symptoms should patients be counselled about to help identify and mitigate the risk of hyperglycemia? (check all that apply)

|   |   | Sign/symptom of
hyperglycemia |
|---|---|----------------------------------|
| А | Excessive thirst [KEY QUESTION]                           | 1                                |
| В | Increased frequency or amount of urination [KEY QUESTION] | ~                                |
| С | Increased appetite with weight loss
[KEY QUESTION]     | 1                                |
| D | Inability to swallow                                      |                                  |
| E | Yellowing of the skin                                     |                                  |
| F | Difficulty breathing [KEY QUESTION]                       | ~                                |
| G | Nausea and/or vomiting [KEY QUESTION]                     | 1                                |
| Η | Headache [KEY QUESTION]                                   | 1                                |
| Ι | I don't know/am not sure                                  |                                  |

[ON-LINE SURVEY - PROGRAMMER: RANDOMIZE THE ORDER OF THESE 8 QUESTIONS] 6. Which of the following is NOT a risk factor for patients to develop hyperglycemia when receiving treatment with Piqray?

□ Diabetic or pre-diabetic
 □ Fasting glucose >250 mg/dL (13.9 mmol/L)
 ✓ Body mass index <30 kg/m^2
 □ Age ≥75 years
 □ I don't know/am not sure

#### [ON-LINE SURVEY - PROGRAMMER: RANDOMISE THE ORDER OF THE FIRST 4 RESPONSE OPTIONS]

7. According to the Piqray Prescriber's/HCP Guide for Hyperglycemia and SmPC for Piqray, please indicate if the following statement is True or False: For patients at higher risk for developing hyperglycemia, there is no need to consult with a healthcare professional or endocrinologist experienced in the treatment of hyperglycemia.

🗆 True

✓ False

□ I don't know/am not sure

8. According to the Piqray Prescriber's/HCP Guide for Hyperglycemia and SmPC for Piqray, to mitigate risk of hyperglycemia, which of the following should be performed before a patient starts treatment with Piqray?

|   |  | Check the box if
the action should
be performed |
|---|--|---|
| Α | Obtain a fasting glucose and
HbA1c  | 1   |
| В | Optimize the patient's level of
blood glucose, as applicable                      | 1   |
| с | Counsel the patient about the risk of hyperglycemia                                  | 1   |
| D | Increase the dose of their current
antihyperglycemic medication, if
applicable |   |
| E | Consult with a diabetologist for
all patients, even if they are not
diabetic   |   |
| F | I don't know/am not sure   |   |

[ON-LINE SURVEY - PROGRAMMER: RANDOMIZE THE ORDER OF THESE 5 QUESTIONS]  According to the Piqray Prescriber's/HCP Guide for Hyperglycemia and SmPC for Piqray, please indicate if the following statement is True or False: The monitoring schedule of fasting glucose levels for patients receiving Piqray is the same for patients with, and without, risk factors for hyperglycemia.

D True

✓ False

□ I don't know/am not sure

10. According to the Piqray Prescriber's/HCP Guide for Hyperglycemia and SmPC for Piqray, at what frequency should fasting glucose testing be performed for all patients treated with Piqray?

□ Weekly for the first 3 months of treatment, then monthly thereafter

✓ At weeks 1, 2, 4, 6, and 8 after treatment start, then monthly thereafter □ Daily for the first 2 weeks of treatment, then at Weeks 4, 6, and 8, then monthly thereafter

□ I don't know/am not sure

[ON-LINE SURVEY - PROGRAMMER: RANDOMIZE THE ORDER OF THE FIRST 3 RESPONSE OPTIONS]

11. According to the Piqray Prescriber's/HCP Guide for Hyperglycemia and SmPC for Piqray, at what frequency should HbA1c testing be performed for all patients treated with Piqray?

Monthly for the first 3 months of treatment, then quarterly thereafter
 4 weeks after treatment start, then every 3 months thereafter
 Monthly for the first 6 months of treatment, then annually thereafter
 I don't know/am not sure

[ON-LINE SURVEY - PROGRAMMER: RANDOMIZE THE ORDER OF THE FIRST 3 RESPONSE OPTIONS]

 According to the Piqray Prescriber's/HCP Guide for Hyperglycemia and SmPC for Piqray, please indicate if the following statement is True or False: For fasting glucose values that are ≤250 mg/dL (≤13.9 mmol/L), no Piqray dose adjustment is required. It is recommended to manage by initiating or intensifying oral antihyperglycemic treatment.

🖌 True

🗆 False

□ I don't know/am not sure

- 13. According to the Piqray Prescriber's/HCP Guide for Hyperglycemia and SmPC for Piqray, which of the following fasting glucose values (blood) that are elevated (above the upper limit of normal) require Piqray dosing to be interrupted?
  - Any fasting glucose value >160 mg/dL (>8.9 mmol/L)
  - □ Any fasting glucose value >200 mg/dL (>27.8 mmol/L

□ Any fasting glucose value >200 mg/dL (>27.8 mmol/L

Any fasting glucose value >250 mg/dL (>13.9 mmol/L)

□ I don't know/am not sure

